15.3. MedDRA queries for identifying AESIs

The tables below are MedDRA version specific and may be revised with a new MedDRA version:

Table 15.3 1: Preferred terms for AESIs which are not pl	MDs
--	-----

	Autoimmune myocarditis
	Eosinophilic myocarditis
Mucoorditio	Giant cell myocarditis;
Myocarditis	Hypersensitivity myocarditis
	Immune-mediated myocarditis
	Myocarditis
	Autoimmune pericarditis
	Pericarditis
Pericarditis	Pericarditis adhesive
	Pericarditis constrictive
	Pleuropericarditis
Severe Hypersensitivity	Grade 3 unsolicited AEs under MedDRA SMQ hypersensitivity, narrow search
	(includes anaphylaxis), with an onset within 24 hours after vaccination

COVID 19 infection will be based on PCR test (there is no MEDRA query)

Event Category	Immune-Mediated Disorder	MedDRA PT	PT Code
Neuroinflammatory	Cranial nerve disorders and	Anosmia	10002653
disorders	inflammations	IIIrd nerve paralysis	10021283
		IIIrd nerve paresis	10054202
		IVth nerve paralysis	10023110
		IVth nerve paresis	10054201
		Trigeminal palsy	10049788
		Trigeminal nerve paresis	10068008
		VIth nerve paralysis	10047641
		VIth nerve paresis	10071044
		Facial paralysis	10016062
		Facial paresis	10051267
		Acoustic neuritis	10063162
		Glossopharyngeal nerve paralysis	10051270
		Tongue paralysis	10031270
		Vagus nerve paralysis	10043572
		Vocal cord paralysis	10004001
		Vocal cord paresis	10047074
		XIth nerve paralysis	10049234
		Hypoglossal nerve paralysis	10048842
		Hypoglossal nerve paresis	10067129
		Bulbar palsy	10006542
		Oculofacial paralysis	10030069
		Neuritis cranial	10029244
		Cranial nerve disorder	10061093
		Paresis cranial nerve	10061911
		Cranial nerve paralysis	10061908
		Cranial nerve palsies multiple	10011314
		Optic neuritis	10030942
	Multiple sclerosis	Multiple sclerosis	10028245
		Radiologically isolated syndrome	10079292
		Primary progressive multiple sclerosis	10063401
		Progressive multiple sclerosis	10053395
		Marburg's variant multiple sclerosis	10067067
		Secondary progressive multiple sclerosis	10063400
		Multiple sclerosis relapse	10048393
		Relapsing multiple sclerosis	10080700
		Multiple sclerosis relapse prophylaxis	10070495
		Progressive relapsing multiple sclerosis	10067063
		Relapsing-remitting multiple sclerosis	10063399
		Tumefactive multiple sclerosis	10078556
		Expanded disability status scale score decreased	10071385
		Expanded disability status scale score decreased	10071384
	Myelitis / Transverse myelitis	Myelitis transverse	10071564
	ingentis / fransverse myentis	Myelitis	10028524
		Acute flaccid myelitis	10028524
		Noninfectious myelitis	10082097
	Guillain-Barré syndrome	Guillain-Barré syndrome	100/1/64
	Sumani-Barre Synuronne		
	A outo diagonain-t-1	Miller Fisher syndrome	10049567
	Acute disseminated	Demyelination	10012305
	encephalomyelitis and	Intramyelinic oedema	10083038
	demyelination (including site	Autoimmune demyelinating disease	10075688
	specific variants)	Clinically isolated syndrome	10071068
		Leukoencephalomyelitis	10048999
		Leukoencephalopathy	10024382
		Acute disseminated encephalomyelitis	10000709
		Acute haemorrhagic leukoencephalitis	10058994

Table 15.3 2: Preferred terms for AESIs which are pIMDs

			10010050
		Concentric sclerosis	10010252
		Encephalitis periaxialis diffusa	10049020
		Limbic encephalitis	10078012
		Neuromyelitis optica spectrum disorder	10077875
		Neuromyelitis optica pseudo relapse	10080353
		Autoimmune encephalopathy	10075691
		Bickerstaff's encephalitis	10076985
		Noninfective encephalitis	10074712
		Encephalitis autoimmune	10072378
		Immune-mediated encephalitis	10083074
		Rasmussen encephalitis	10071141
		Encephalitis allergic	10056387
		Encephalitis brain stem	10048997
		Encephalitis haemorrhagic	10014589
		Encephalomyelitis	10014619
		Noninfective encephalomyelitis	10074713
		Encephalitis post immunisation	10014602
		Panencephalitis	10056332
		Encephalitis toxic	10014607
		Chronic lymphocytic inflammation with pontine perivascular	10075197
		enhancement responsive to steroids	10010171
	Myasthenia gravis	Myasthenia gravis	10028417
	1.1 uotienta Bravio	Myasthenia gravis crisis	10023417
		Ocular myasthenia	10049168
		Myasthenic Syndrome	10049100
	Autoimmune / Immune-	Autoimmune neuropathy	1002042
	mediated peripheral	Immune-mediated neuropathy	10070439
	neuropathies and plexopathies	Neuritis	
	neuropatities and prexopatities		10029240
		Anti-myelin-associated glycoprotein associated	10078324
		polyneuropathy	1000170
		Subacute inflammatory demyelinating polyneuropathy	10081726
		Chronic inflammatory demyelinating polyradiculoneuropathy	10057645
		Lewis-Sumner syndrome	10065580
		Demyelinating polyneuropathy	10061811
		Polyneuropathy idiopathic progressive	10036111
		Multifocal motor neuropathy	10065579
		Acute motor-sensory axonal neuropathy	10076657
		Acute motor axonal neuropathy	10076658
		Cervical neuritis	10008293
		Mononeuritis	10027910
		Mononeuropathy multiplex	10027918
		Brachial plexopathy	10065417
		Radiculitis brachial	10037778
		Neuralgic amyotrophy	10029229
	Narcolepsy	Narcolepsy	10029223
Iusculoskeletal	Systemic lupus erythematosus	Systemic lupus erythematosus	10023713
isorders	Systemic rupus orymematosus	SUE arthritis	10042945
		Cutaneous lupus erythematosus	10040908
		Acute cutaneous lupus erythematosus	10036309
		Chronic cutaneous lupus erythematosus	10057929
		Subacute cutaneous lupus erythematosus	10057903
		Lupus cystitis	10074714
		Lupus encephalitis	10025130
		Lupus endocarditis	10058225
		Lupus enteritis	10067738
		Lupus hepatitis	10067737
		Lupus myocarditis	10066391
		Lupus myositis	10079642
		Lupus myositis	10079042

		Lupus pancreatitis	10067750
		Lupus pleurisy	10073694
		Lupus pneumonitis	10057481
		Lupus-like syndrome	10050551
		Neuropsychiatric lupus	10063663
		Central nervous system lupus	10076328
		Pericarditis lupus	10058149
		Peritonitis lupus	10062898
		Systemic lupus erythematosus rash	10042946
		Systemic lupus erythematosus disease activity index abnormal	10067659
		Systemic lupus erythematosus disease activity index	10067658
		decreased	
		Systemic lupus erythematosus disease activity index increased	10067657
Systemic Scl		Scleroderma	10039710
(Systemic scl	erosis)	Scleroderma renal crisis	10062553
		Scleroderma associated digital ulcer	10073229
		Reynold's syndrome	10070953
		Systemic sclerosis pulmonary	10042954
		Systemic scleroderma	10078638
		Anti-RNA polymerase III antibody increased	10082280
		Anti-RNA polymerase III antibody positive	10082283
		CREST syndrome	10011380
Muscular Au		Polymyalgia rheumatica	10036099
Immune-med	iated disorders	Dermatomyositis	10012503
		Polymyositis	10036102
		Autoimmune myositis	10082418
		Immune-mediated myositis	10083073
		Juvenile polymyositis	10076673
		Antisynthetase syndrome	10068801
Rheumatoid a		Rheumatoid arthritis	10039073
associated co	nditions	Autoimmune arthritis	10071155
		Immune-mediated arthritis	10083155
		Laryngeal rheumatoid arthritis	10059669
		Rheumatoid lung	10039081
		Rheumatoid scleritis	10067427
		Rheumatic brain disease	10079411
		Rheumatoid neutrophilic dermatosis Rheumatoid nodule	10072362
		Juvenile idiopathic arthritis	10048694 10059176
		•	10056667
		Cogan's syndrome Palindromic rheumatism	10036667
		Still's disease	10033334
Spondyloarth	ropathies	Arthritis reactive	10042001
Spondyloarth	ropaulies	Reiter's syndrome	10003207
		Ankylosing spondylitis	10002556
		Spondylitis	10061371
		Spondyloarthropathy	10051265
		Juvenile spondyloarthritis	10076675
		Enteropathic spondylitis	10076549
		Psoriatic arthropathy	10070349
		Juvenile psoriatic arthritis	10076674
Relapsing po	lychondritis	Polychondritis	10065159
	ctive tissue disease	Overlap syndrome	10068786
		Mixed connective tissue disease	10003780
Gout		Gout	10027734
			1001002/
Court		Gouty arthritis	10018634

Gastrointestinal	Inflammatory Bowel disease	Crohn's disease	10011401
disorders	5	Colitis ulcerative	10009900
		Colitis microscopic	10056979
		Autoimmune colitis	10075761
		Immune-mediated enterocolitis	10078961
		Inflammatory bowel disease	10021972
		Arthritis enteropathic	10003253
		Proctitis ulcerative	10036783
		Autoimmune enteropathy	10081456
	Autoimmune / Immune-	Autoimmune pancreatitis	10069002
	mediated pancreatitis	Immune-mediated pancreatitis	10083072
	Celiac disease	Coeliac disease	10009839
Liver disorders	Autoimmune / Immune-	Autoimmune hepatitis	10003827
	mediated hepatobiliary diseases	Immune-mediated hepatitis	10078962
		Biliary cirrhosis primary	10004661
		Primary biliary cholangitis	10080429
		Cholangitis sclerosing	10008609
Endocrine and	Autoimmune / immune-	Autoimmune hypothyroidism	10076644
Metabolic	mediated thyroid diseases	Immune-mediated hypothyroidism	10083075
disorders		Atrophic thyroiditis	10077172
		Autoimmune thyroiditis	10049046
		Immune-mediated thyroiditis	10083071
		Silent thyroiditis	10079012
		Hashimoto's encephalopathy	10069432
		Hashitoxicosis	10067873
		Basedow's disease	10004161
		Marine Lenhart syndrome	10068828
		Autoimmune thyroid disorder	10079165
	Autoimmune / Immune-	Autoimmune endocrine disorder	10078953
	mediated endocrinopathy (NOS)	Immune-mediated endocrinopathy	10078964
	Diabetes mellitus type I	Type 1 diabetes mellitus	10067584
		Fulminant type 1 diabetes mellitus	10072628
	Polyglandular autoimmune	Polyglandular autoimmune syndrome type I	10036072
	syndrome	Polyglandular autoimmune syndrome type II	10036073
		Polyglandular autoimmune syndrome type III	10064115
	Autoimmune hypophysitis	Lymphocytic hypophysitis	10063685
	Addison's disease	Addison's disease	10001130
Skin disorders	Psoriasis	Psoriasis	10037153
	Vitiligo	Vitiligo	10047642
	Erythema nodosum	Erythema nodosum	10015226
	Alopecia areata	Alopecia areata	10001761
	Lichen planus	Lichen planopilaris	10081142
		Lichen planus	10024429
	Sweet's syndrome	Acute febrile neutrophilic dermatosis	10000748
	Autoimmune / Immune-	Pemphigus	10034280
	mediated bullous skin diseases	Pemphigoid	10034277
		Dermatitis herpetiformis	10012468
		Autoimmune dermatitis	10075689
		Immune-mediated dermatitis	10083156
	Localised Scleroderma	Morphoea	10027982

Vasculitides	Vasculitis and vasculitides	Acute haemorrhagic oedema of infancy	10070599
		Administration site vasculitis	10075969
		Anti-neutrophil cytoplasmic antibody positive vasculitis	10050894
		Aortitis	10002921
		Application site vasculitis	10076027
		Arteritis	10003230
		Arteritis coronary	10003232
		Behcet's syndrome	10004213
		Capillaritis	10068406
		Central nervous system vasculitis	10081778
		Cerebral arteritis	10008087
		Chronic pigmented purpura	10072726
		Cutaneous vasculitis	10011686
		Diffuse vasculitis	10012978
		Eosinophilic granulomatosis with polyangiitis	10078117
		Erythema induratum	10015213
		Granulomatosis with polyangiitis	10072579
		Haemorrhagic vasculitis	10071252
		Henoch-Schonlein purpura	10019617
		Henoch-Schonlein purpura nephritis	10069440
		Hypersensitivity vasculitis	10020764
		Injection site vasculitis	10067995
		Kawasaki's disease	10023320
		Langerhans' cell histiocytosis	10069698
		Lupus vasculitis	10058143
		MAGIC syndrome	10078132
		Microscopic polyangiitis	10063344
		Nodular vasculitis	10029491
		Ocular vasculitis	10066926
		Optic ischaemic neuropathy	10030924
		Optic neuropathy	10061323
		Polyarteritis nodosa	10036024
		Pulmonary vasculitis	10037457
		Renal arteritis	10038373
		Renal vasculitis	10038546
		Retinal vasculitis	10038905
		Rheumatoid vasculitis	10048628
		Segmented hyalinising vasculitis	10067527
		Takayasu's arteritis	10043097
		Temporal arteritis	10043207
		Thromboangiitis obliterans	10043540
		Urticarial vasculitis	10048820
		Vaccination site vasculitis	10076191
		Vascular purpura	10047097
		Vasculitic rash	10047111
		Vasculitic ulcer	10075714
		Vasculitis	10047115
		Vasculitis gastrointestinal	10048319
		Vasculitis necrotising	10047124
Other	Stevens-Johnson syndrome	Stevens-Johnson syndrome	10042033
	-	Erythema multiforme	10015218
		Toxic epidermal necrolysis	10044223
		SJS-TEN overlap	10083164
	Blood autoimmune / immune-	Autoimmune anaemia	10080243
	mediated disoders	Autoimmune haemolytic anaemia	10073785
		Warm type haemolytic anaemia	10047822
		Cold type haemolytic anaemia	10009868
		Coombs positive haemolytic anaemia	10010941
		Evans syndrome	10053873

	Immune thrombocytopenic purpura	10074667
	Thrombocytopenic purpura	100/400/
	Thrombocytopenic purpura	10043648
	Autoimmune aplastic anaemia	10043048
	Autoimmune neutropenia	10071370
	*	10055128
	Autoimmune pancytopenia	
	Immune-mediated pancytopenia	10083004
	Antiphospholipid syndrome	10002817
	Pernicious anaemia	10034695
Autoimmune / immune-	Glomerulonephritis rapidly progressive	10018378
mediated glomerulonephritis	IgA nephropathy	10021263
	IgM nephropathy	10077209
	C1q nephropathy	10081461
	Glomerulonephritis membranous	10018372
	Glomerulonephritis membranoproliferative	10018370
	Membranous-like glomerulopathy with masked IgG-kappa	10083098
	deposits	100((452
	Mesangioproliferative glomerulonephritis	10066453
	Anti-glomerular basement membrane disease	10081981
	Autoimmune nephritis	10077087
	Immune-mediated nephritis	10083070
	Chronic autoimmune glomerulonephritis	10073016
	Tubulointerstitial nephritis and uveitis syndrome	10069034
Ocular autoimmune / immune-	Uveitis	10046851
mediated diseases	Vogt-Koyanagi-Harada disease	10082001
	Ocular pemphigoid	10067776
	Autoimmune retinopathy	10071578
	Acute macular outer retinopathy	10079367
	Autoimmune uveitis	10075690
	Immune-mediated uveitis	10083069
	Autoimmune eye disorder	10081123
Autoimmune / immune-	Autoimmune myocarditis	10064539
mediated heart disease	Immune-mediated myocarditis	10082606
	Autoimmune pericarditis	10079058
Sarcoidosis	Sarcoidosis	10039486
	Pulmonary sarcoidosis	10037430
	Neurosarcoidosis	10037430
	Cutaneous sarcoidosis	10078011
	Liver sarcoidosis	10068664
	Muscular sarcoidosis	
		10028365
0'" 1	Ocular sarcoidosis	10065700
Sjögren's syndrome	Sjogren's syndrome	10040767
Autoimmune lung disease	Idiopathic pulmonary fibrosis	10021240
	Idiopathic interstitial pneumonia	10078268
	Interstitial lung disease	10022611
	Pulmonary fibrosis	10037383
	Autoimmune lung disease	10080701
	Immune-mediated pneumonitis	10082452
Goodpasture's syndrome	Goodpasture's syndrome	10018620
Raynaud's phenomenon	Raynaud's phenomenon	10037912

Note: This list is reviewed for each new MedDRA version and the list applicable at database lock will be documented within the ADAM package.

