6.1.1.1.4 Adverse Events of Special Interest

An AESI (serious or nonserious) is defined as an AE or SAE of scientific and medical concern specific to the sponsor's product or program, for which ongoing monitoring and rapid communication by the investigator to the sponsor could be appropriate (ICH E2F; CIOMS VI).

For this study, AESIs will include the following events:

- Virologically confirmed SARS-CoV-2 infections (see Section 6.6 for disease definitions)
- Potential immune-mediated disorders (Appendix 13.4)
- Anaphylaxis or severe hypersensitivity within 24 hours after study vaccine administration
- Pericarditis or myocarditis

Refer to Section 6.1.1.3.1 for reporting AESIs.

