6.1.1.3.1 Reporting Serious Adverse Events and Adverse Events of Special Interest

Any AE that meets SAE criteria (Section 6.1.1.1.2) must be reported to PPD Pharmacovigilance within 24 hours after site personnel first learn of the event. Events should be captured electronically in the EDC system; however, if the EDC is unavailable, a backup paper option is available and this form can be faxed to the fax number listed below.

SAE [contact] [contact]

Any AE that meets AESI criteria (Section 6.1.1.1.4) must be reported to PPD Pharmacovigilance within 24 hours after site personnel first learn of the event.

If the EDC is unavailable and a faxed form is used to report an SAE or AESI, the site should update the EDC with exactly the same information reported on paper (by fax) as soon as possible after the EDC becomes available again.

The sponsor has a legal responsibility to notify both the local regulatory authority and other regulatory agencies about the safety of an IP under clinical investigation. The sponsor will comply with country-specific regulatory requirements relating to safety reporting to the regulatory authority, IRB/IEC, and investigators.

An investigator who receives an investigator safety report describing an SAE or other specific safety information from the sponsor will review and then file it as appropriate and will notify the IRB/IEC according to local requirements.

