6.1.2 Clinical Safety Laboratory Assessments

The following laboratory assessments will be performed at the time points specified in the SOE (Table 13-1):

Hematology: Basophils, eosinophils, erythrocytes (red blood cells), hemoglobin,

leukocytes (white blood cells), lymphocytes, monocytes,

neutrophils, and platelets

Chemistry: Bilirubin (total and direct), alkaline phosphatase, alanine

aminotransferase, aspartate aminotransferase, blood urea nitrogen,

creatinine, and uric acid

SARS-CoV-2: • SARS-CoV-2 serology (Ab), which will include S and N protein

for prevaccination timepoints and N protein for postvaccination

timepoints to monitor for undetected SARS-CoV-2 infections

• SARS-CoV-2 RT-PCR (nasal swab)

HIV/HBV/HCV • Hepatitis B surface antigen test

• HIV 4th generation antigen/Ab test

• Anti-HCV test

Other analyses: Female participants of childbearing potential:

β-human chorionic gonadotropin (serum test at Screening; urine

test at additional time points)

Serum FSH, to confirm postmenopausal status (Section 13.2)

The clinical safety laboratory assessments will be performed by a local or central laboratory as detailed in the Laboratory Manual. Screening laboratory tests and SARS-CoV-2 RT-PCR may be repeated once for enrollment requirements.

The investigator must review the laboratory reports, document this review, and record any clinically relevant changes occurring during the study. If the laboratory reports are not transferred electronically, the values must be filed with the source information (including reference ranges). Any clinically relevant laboratory results should be reported as an AE or SAE, as appropriate, using the AE intensity grading (Section 6.1.1.2.1).

All laboratory tests with values considered clinically significantly abnormal during participation in the study should be repeated until the values return to normal or baseline or are no longer considered clinically significant by the investigator or medical monitor. If such values do not return to normal/baseline within a period of time judged reasonable by the investigator, the etiology should be identified, and the sponsor notified.

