6.6 SARS-CoV-2 and COVID-19 Disease Assessment and Definitions

Vaccine efficacy will not be evaluated in this study, but all virologically confirmed SARS-CoV-2 infections should be reported by the participant and documented as clinical events as well as AESIs (Section 6.1.1.1.4). Any available isolate genotyping results will also be requested. Participants will be instructed to inform the investigator in the event of a positive SARS-CoV-2 diagnostic test. Clinical serology testing, including N protein, will be performed at Screening, Day 1, Day 85, and Day 180 to monitor for undetected SARS-CoV-2 infections. A nasal (nasopharyngeal or mid-turbinate) swab sample is scheduled for SARS-CoV-2 RT-PCR testing at Screening and Day 1. The screening sampling and SARS-CoV-2 RT-PCR testing must be performed within the 7 days before Day 1.

All participants with suspected COVID-19 are required to have an unscheduled visit for suspected COVID-19. At this visit, participants will undergo the following assessments:

- Medical history
- SARS-CoV-2 RT-PCR (nasal swab [nasopharyngeal or mid-turbinate])
- Physical examination
- Vital sign measurements
- Review of adverse events
- Concomitant medication/vaccination

All participants with confirmed COVID-19 are required to have an unscheduled COVID-19 convalescent visit. At this visit, participants will undergo the following assessments:

- Medical history
- Physical examination
- Vital sign measurements
- COVID-19 evaluation
- Review of adverse events
- Concomitant medication/vaccination

To complete the COVID-19 evaluation, the investigator will review the history of the participants, including medical records to define the severity of COVID-19. Any virologically confirmed cases of SARS-CoV-2 infection or COVID-19 during the study will be assigned one of the following definitions:

Asymptomatic	Virologically confirmed SARS-CoV-2 by RT-PCR or N protein
SARS-CoV-2	seroconversion without any of the following symptoms: fever or
infection:	chills, cough, shortness of breath or difficulty breathing, fatigue,
	muscle or body aches, headache, new loss of taste or smell, sore

throat, congestion or runny nose, nausea or vomiting, diarrhea

taste or smell, sore throat, congestion or runny nose, nausea or

Symptomatic Virologically confirmed by RT-PCR and include one or more of the COVID-19: following: fever or chills, cough, shortness of breath or difficulty breathing, fatigue, muscle or body aches, headache, new loss of

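### SAP 15.3 identifies the COVID-19 AESI by PCR only, against protocol 6.6 and SAP 8.4, with no onset rule for serology-only cases; separately, two of three SAP 4 intervals contradict the study-day formula

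*SAP*

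**What the plan says.** The percentage of participants with AESIs is part of a primary endpoint (protocol 2, SAP 2.1). Protocol 6.1.1.1.4 lists among the AESIs "Virologically confirmed SARS-CoV-2 infections (see Section 6.6 for disease definitions", and SAP 9.1.6 repeats the item with the same pointer to protocol 6.6.

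Protocol 6.6 defines asymptomatic infection as "Virologically confirmed SARS-CoV-2 by RT-PCR or N protein" seroconversion, without any listed symptom. Symptomatic COVID-19 is "Virologically confirmed by RT-PCR and include one or more of the" listed symptoms. It also says that confirmed infections are to be "documented as clinical events as well as AESIs".

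SAP 9.1.6 identifies AESIs by MedDRA query or by the investigator on the eCRF, and sends the reader to appendix 15.3 for the queries. There, the rule for COVID-19 is "COVID 19 infection will be based on PCR test (there is no MEDRA query". SAP 8.4, which is headed as an AESI analysis, counts in item 2 any laboratory-confirmed infection, symptomatic or not, by RT-PCR or N-protein seroconversion. It runs from vaccination to the end of the study.

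On timing, SAP 9.1.6 tabulates AESIs by onset in Day 1-28 and Day 1-180. SAP 4 makes the vaccination day Day 1. It describes the AE intervals as the vaccination day plus 6, 28 or 180 further days, labelled as ending on Day 7, Day 28 and Day 180.

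**The concern.** The appendix that puts the AESI definition into practice is narrower than the definition. The cases it leaves out are the silent infections that the serology schedule is there to find. Two SAP tables, both described as AESI analyses, can then show different infection counts for the same dose group, and the narrower count feeds a primary endpoint. SAP 13 declares no change to the planned analysis, so the PCR-only line cannot be read as a deliberate departure.

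The onset windows add a second gap. A seroconversion has a sample date but no observed onset, and the public SAP text does not say which date to use. The windows themselves are described in SAP 4 by a day count that does not match its label.

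**Working it through.** **Definitions side by side**

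| Place | What counts as the COVID-19 AESI |
|---|---|
| Protocol 6.1.1.1.4 and SAP 9.1.6 | As defined in protocol 6.6 |
| Protocol 6.6 | Symptomatic: RT-PCR. Asymptomatic: RT-PCR or N seroconversion |
| SAP 8.4 item 2 | RT-PCR or N seroconversion, with or without symptoms |
| SAP 15.3 | PCR |

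Only 15.3 leaves out seroconversion.

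**Tests after vaccination.** Protocol 6.6: "A nasal (nasopharyngeal or mid-turbinate) swab sample is scheduled for SARS-CoV-2 RT-PCR testing at Screening and Day 1". The schedules of events (protocol Table 13-1, SAP 15.1) agree: no RT-PCR is scheduled after Day 1. Later swabs are taken at a visit for suspected COVID-19 or when clinically indicated. N serology is scheduled at Day 85 and Day 180, and at an early termination visit. An infection without symptoms will therefore usually be seen by serology alone.

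**Routes for a serology-only case**
- SAP 8.4 item 2: counted from the laboratory result, with no Day 180 limit.
- SAP 9.1.6 through 15.3: not found, because there is no PCR result and no MedDRA query.
- SAP 9.1.6 through the investigator: counted if the site reports it as an AESI.

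The 9.1.6 table therefore depends on site reporting, and the 8.4 table does not.

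**Which onset window**
- Day 85 ± 5 gives Day 80-90. Dated by sample, the case is in Day 1-180 only.
- Day 180 ± 7 gives Day 173-187, which is 15 permitted days. Of these, 7 (Day 181-187) are after Day 180. Dated by sample on one of them, the case is in neither window. If the end is taken as Day 181, from the SAP 4 day count, 6 of the 15 days remain outside.
- Onset entered as wholly unknown: SAP 9.1 imputes the vaccination date, so the case is on Day 1 and in both windows.

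**Size.** SAP 9.1 bases percentages on the Safety Set within each dose group. One case missing from 9.1.6, in a participant with no other AESI, changes the percentage by 1/30 = 3.3 points at the planned size. SAP 12 says that the study closed early. If a dose group ended with 20 or 10 participants (assumed sizes), the change is 1/20 = 5.0 or 1/10 = 10.0 points. The documents give no seroconversion rate, so the number of such cases is left open.

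**SAP 4 day counts.** Study day = assessment date − injection date + 1, so k subsequent days end on Day k + 1.

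| Interval | k | k + 1 | Label | Agrees |
|---|---|---|---|---|
| Solicited | 6 | Day 7 | Day 7 | Yes |
| Unsolicited | 28 | Day 29 | Day 28 | No |
| MAAE, AESI, SAE | 180 | Day 181 | Day 180 | No |

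**The case against.** The strongest reply is that nothing is lost. SAP 8.4 already reports serology-only infections by dose group, including those first found at a late final visit. Sites also have a duty to report them. Protocol 6.1.2 says "The investigator must review the laboratory reports, document this review, and record any clinically relevant changes occurring during the study", and protocol 6.1.1.3.1 says "Any AE that meets AESI criteria (Section 6.1.1.1.4) must be reported to PPD Pharmacovigilance within 24 hours" of awareness. SAP 9.1.6 accepts investigator-identified AESIs and says that AESIs are reported until exit from the study. This stands in large part. A reader might infer that the SAP is PCR-only throughout, or that serology-only infections go unreported. Neither is supported. What remains is that the 9.1.6 percentage relies on complete site reporting for these cases and 8.4 does not. Even with complete reporting, 9.1.6 cuts onset at Day 180 and 8.4 does not.

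A reader might also infer that serology-only cases will pile up on Day 1. Protocol 6.1.1.3 asks for an onset time for every AE, so the SAP 9.1 imputation applies only where a site leaves onset unknown or gives a partial date in the month or year of vaccination. That is a gap to close, not an expected result.

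On the day counts, it is tempting to say that every SAP 4 interval is wrong, or that the two in conflict are a day too long. The solicited interval is right. For the other two, the documents do not settle which side is the error. Protocol 2 and 6.1.1.2 speak of 28 days after vaccination, which is Day 29 by the SAP formula, whereas SAP 2.1 labels the period Day 1 through Day 28.

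Finally, 3.3 points is simply the weight of one participant in 30. That is true, and it is offered only as the size per case.

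**Conclusion.** The conflict is real: the PCR-only rule in SAP 15.3 contradicts protocol 6.6, SAP 9.1.6 and SAP 8.4 item 2. It should be corrected because it feeds a primary endpoint. The 9.1.6 and 8.4 counts can differ by one participant for each serology-only case that is not reported as an AESI: 3.3 points at 30 per dose group, if that participant has no other AESI. The absence of a dating rule is a smaller gap in the same place, judged on the public SAP text only. The SAP 4 mismatch is a separate one-day inconsistency in two of the three intervals. Protocol 7.1 plans no hypothesis test, so the effect is confined to descriptive safety rates.

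**What to change.** **SAP 15.3.** Identify the COVID-19 AESI by RT-PCR or N-protein seroconversion, with seroconversion meaning N-negative at baseline and N-positive after vaccination. Leave SAP 8.4 item 2 as broad as it is. Imposing the protocol 6.6 split on item 2 would drop a symptomatic participant who seroconverts without a positive PCR. Item 2 counts that participant now, whereas neither the symptomatic nor the asymptomatic category in 6.6 does.

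**Onset.** Date a serology-only case by the collection date of the first post-baseline N-positive sample, and note that this is a detection date. Exempt these cases from the SAP 9.1 vaccination-date imputation. Include those first found at a final visit after Day 180, so that 9.1.6 and 8.4 agree.

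**SAP 4.** Reconcile count and label with the protocol's period of 28 days after vaccination, and use one convention throughout: either 27 and 179 subsequent days with Day 28 and Day 180, or 28 and 180 subsequent days with Day 29 and Day 181. The solicited line needs no change.

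The cost is SAP wording and programming, with no new data collection. Reported AESI percentages may rise.
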